Each participant will swish 15 mL (one tablespoon) of the Viscous Lidodan 2% in their mouth for 60 seconds, then spit into a sink. This amount is the recommended manufacturer dosage. This will occur once during the one collection session. Viscous Lidodan 2% (i.e., Lidocaine Hydrochloride Oral Topical Solution 2% USP) is a topical anesthetic. The numbing effects of Viscous Lidodan 2% should take effect after five minutes and last around 30 minutes.

No other topical oral anesthetics are permitted to have been administered in the day before the trial. No details are required on any other medications.

Safety Assessment

Safety Assessment/Monitoring and Risk Mitigation. Each participant completes a pre-collection questionnaire where it asks all subjects to report any personal or family history of adverse reactions to anesthetics. This is a hard-copy questionnaire that is completed by the participant after the informed consent form, but before collection begins. It is reviewed together with the experimenter and participant before collection commences. Participants will be informed prior to beginning the experiment that they may withdraw at any time. They will be monitored throughout the experiment by research staff for signs of distress or adverse reactions (e.g., redness, itching or swelling of skin, hives, burning, stinging, or any other skin problems, swelling of the neck area, or any difficulty with breathing). The QI will be available via phone/pager during administration of Lidocaine in case of adverse event(s) for assessment/ triage/treatment/follow-up as clinically indicated.

If any reactions or adverse effects (i.e., redness, itching or swelling of skin, hives, burning, stinging, or any other skin problems, swelling of the neck area, or any difficulty with breathing)

are observed by the experimenters during collection, the QI will be called and the experimenter will escort the participant to the hospital emergency room connected to the Clinical Sciences Building. After the collection session is over, the participant will be instructed to report to their nearest emergency room if they experience any reactions or adverse effects. Participants will be informed that they should avoid eating and drinking and exposure to extreme hot or cold temperatures (e.g. food, drink) until complete sensation has returned. The numbness may also increase the risk of unintentional biting (e.g., cheek).

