The lidocaine condition will always be lastly completed so its effects will not interfere with the other conditions. Each participant will be asked to complete a questionnaire after collection to localize and rank their numbness on a provided schematic. And adverse events reported by the participant will be recorded on this document and reported immediately to the qualified investigator. After the collection session is over, the participant will be instructed to report to their nearest emergency room if they experience any reactions or adverse effects. Topical anesthetics in the mouth may impair swallowing. The numbness may also increase the risk of unintentional biting (e.g., cheek). The qualified investigator, an otolaryngology head and neck surgeon, will follow-up with the subject as she deems appropriate. All serious unexpected adverse drug reactions (SUSARs) will be reported to Health Canada as mandated per C.05.014 (1) of the FDR.

Budget Considerations

Participants will be offered a small honorarium (\$20.00) for taking part in the study.

Experiment Location

6-104, Clinical Sciences Building, University of Alberta.

Statistical Analysis

Given the between groups nature of the sensorimotor perturbation (i.e., lidocaine vs. no lidocaine groups), we will first run a $2 \times 2 \times 4 \times 2$ ANOVA with group (lidocaine vs. no lidocaine), task (spell vs. sound), word type (exception words, regular words, pseudohomophones, nonwords), and time (pre-lidocaine vs. post-lidocaine), as the factors of interest. If the 4-way interaction is significant, a series of mixed ANOVAs will be run to test the effect of sensorimotor perturbation for each of the reading tasks. The independent variables will be time (pre-perturbation vs. post-perturbation), word type (exception, regular, pseudohomophone, nonword) and group. An ANOVA was also be run to test the effect of the sensorimotor perturbation for the control picture categorization task, with the independent variables including time (pre-perturbation vs. post-perturbation) and group. The dependent variable will include response time and accuracy. Bonferroni corrected t -tests were used to explore significant effects of the lidocaine on task performance. No interim analyses are planned. The data will be analyzed when thirty subjects have participated.

Data | Documents

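### Every planned ANOVA uses a lidocaine versus no-lidocaine group that this within-subjects design does not contain, so the 4-way gate cannot be computed, and dyslexia status, lollipop and bite bar have no model term

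*Combined protocol and SAP*

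**What the plan says.** **Analysis.** Statistical Analysis opens with "Given the between groups nature of the sensorimotor perturbation (i.e., lidocaine vs. no lidocaine groups" and plans a 2 x 2 x 4 x 2 ANOVA. Its factors are group (lidocaine, no lidocaine), task (spell, sound), word type (four levels) and time (before, after lidocaine). The next step is conditional: "If the 4-way interaction is significant, a series of mixed ANOVAs will be run to test the effect of sensorimotor perturbation", one for each reading task. For those follow-up models, "The independent variables will be time (pre-perturbation vs. post-perturbation), word type (exception, regular, pseudohomophone, nonword) and group". The picture task gets its own ANOVA, "with the independent variables including time (pre-perturbation vs. post-perturbation) and group". Bonferroni-corrected t-tests "were used to explore significant effects of the lidocaine on task performance". On timing: "The data will be analyzed when thirty subjects have participated".

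**Design.** The inclusion criteria describe a within-subjects repeated-measures study of 30 adults with dyslexia, plus 30 controls without it. Methodology item 7 lists four conditions: none, lollipop, bite bar and lidocaine. The first three are in random order and lidocaine is fixed last. Under Treatment, "Each participant will swish 15 mL (one tablespoon) of the Viscous Lidodan 2% in their mouth for 60 seconds". Item 8 names no perturbation, lollipop and bite bar as the comparators to lidocaine. The primary endpoint is response time and accuracy for each word type, with and without perturbation.

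**The concern.** The analysis describes a two-arm trial; the rest of the protocol describes a study in which everyone receives everything. If the lidocaine/no-lidocaine factor has only one level in the data, no term containing it can be estimated, and that includes the interaction on which the reading ANOVAs depend. Reading is the primary endpoint.

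Three further gaps follow.

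- Objective 1 asks about three perturbations, but the first model's time factor and the t-tests concern lidocaine only. A two-level factor cannot separate three perturbations in any case.
- The 30 concurrent controls are compared with the dyslexia group in no model. Objective 2, the comparison with the earlier study of typical readers, has no stated analysis either.
- Three conditions precede lidocaine, and the plan does not say which of them, or what combination, forms the pre level.

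Without a usable written model, the analyst must choose factors, baseline, contrasts and multiplicity family after seeing data on two outcomes, four conditions and four word types.

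**Working it through.** The plan states no alpha, power, effect size or sample-size calculation, so there is no figure of its own to reproduce. The check is whether the planned terms can be estimated.

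**1. Is there any no-lidocaine group?** Treatment gives lidocaine to each participant. Randomisation (Methodology items 5, 7 and 9) covers order only. The exclusion criteria require no history of anesthetic reactions in order to complete all conditions, which might suggest that some people skip lidocaine. Methodology item 3 says such people are not enrolled. The level is empty.

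**2. Rank of each planned model** (effect-coded, all interactions, only lidocaine-group rows present):

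| Model | Parameters | Filled cells | Rank | Top-interaction df estimable |
|---|---|---|---|---|
| Group x task x word type x time | 2 x 2 x 4 x 2 = 32 | 16 | 16 | 0 of 1 x 1 x 3 x 1 = 3 |
| Follow-up: group x word type x time | 2 x 4 x 2 = 16 | 8 | 8 | 0 of 1 x 3 x 1 = 3 |
| Picture: group x time | 2 x 2 = 4 | 2 | 2 | 0 of 1 |

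With two real groups the ranks would be 32, 16 and 4.

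**3. Charitable reading.** Suppose group means the within-person condition, so that no lidocaine is always pre and lidocaine is always post. Group then duplicates time, and the ranks are again 16, 8 and 2.

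**4. What survives.** The 16 estimable parameters of the first model are the terms without group: time, task, word type and their interactions. A within-person before/after-lidocaine contrast by task and word type is therefore available.

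**5. Would relabelling group as dyslexia versus control repair the gate?** The Background reports that in typical readers lidocaine sped up phonological but not orthographic decisions. Take an illustrative 30 ms effect in the phonological task only, in dyslexic readers only, equal over word types (an assumption; the Background gives nothing by word type). In the relabelled 2 x 2 x 4 x 2 model:

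- 4-way component: 0, because the effect does not vary by word type.
- Group x task x time component: 30/2³ = 3.75 ms in absolute value, so the pattern sits in a lower-order term that does not open the gate.

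**6. A model that fits the design.** Reader group (2) x condition (4) x task (2) x word type (4) = 64 cells, rank 64, with 1 x 3 x 1 x 3 = 9 df for the 4-way term, all estimable. Picture task: 2 x 4 = 8 cells, rank 8.

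**7. Sample.** 30 + 30 = 60. Methodology agrees: 12 participants are 20% of those recruited, and 12/0.20 = 60. The analysis trigger is 30.

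**8. Sensitivity cost of testing all of Objective 1.** Paired t-test, noncentral t, n = 30 dyslexic readers, assumed two-sided alpha 0.05 divided by the number of tests, 80% power. Effects are in SDs of the within-person difference.

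| Comparisons | Per word type (x 2 tasks x 4 word types x 2 outcomes) | Averaged over word type (x 2 tasks x 2 outcomes) |
|---|---|---|
| Lidocaine vs none (1) | 16 tests, 0.750 | 4 tests, 0.645 |
| Each perturbation vs none (3) | 48 tests, 0.830 | 12 tests, 0.729 |
| Plus lidocaine vs lollipop and vs bite bar (5) | 80 tests, 0.866 | 20 tests, 0.767 |

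**The case against.** **The later models may mean something else by group.** Only the first ANOVA spells out the levels. If group silently became dyslexia versus control afterwards, the follow-up and picture models could be fitted. This is possible, but the section gives one definition and never changes it, and the gate, where the definition is explicit, would still fail.

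**The loss is not total.** This stands. The before/after-lidocaine contrast remains estimable, the picture ANOVA is not gated, and the t-tests are not expressly tied to the 4-way term. The surviving contrast, however, covers lidocaine only, has an undefined baseline and is confounded with order.

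**The zero 4-way component proves less than it seems.** The same ANOVA would estimate the pattern in group x task x time, and equality over word types is assumed. Both points are right. Even so, only the 4-way term opens the reading ANOVAs, so an effect of this shape would not reach them.

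**Order is being studied.** Methodology has 12 participants complete the protocol over two sessions to examine order and fatigue. That helps with fatigue, but nothing says lidocaine stops being last for them.

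**Objective 2 could be a narrative comparison.** Fair; the plan then only needs to say so.

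**The multiplicity family is a choice and has a price.** Also fair. The documents do not require 48 or 80 tests. Under the same assumptions, holding 0.75 SD would need 36 dyslexic readers (48 tests) or 39 (80 tests); holding 0.645 SD would need 38 (12 tests) or 41 (20 tests). The fix adds no participants only if the lower sensitivity is accepted.

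**The 30-subject trigger is a separate matter.** It may refer to the dyslexia cohort. It still needs to be reconciled with 60 recruited.

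**Conclusion.** The concern holds and must be fixed before analysis. As written, half the cells of every planned ANOVA are empty (16 of 32, 8 of 16, 2 of 4), and the gate has 0 of its 3 degrees of freedom, so the follow-up reading ANOVAs cannot be triggered. Dyslexia status appears in no model, and 2 of 3 perturbations have no explicit test.

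This rests on two readings: that each participant receives lidocaine, as Treatment states, and that group keeps its only stated definition in the later models. The failure of the gate needs only the first. None of it depends on alpha, power or effect size; those assumptions enter only the cost figures.

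**What to change.** Rewrite Statistical Analysis as follows.

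1. **Reading model:** reader group (dyslexia, control; between) x condition (none, lollipop, bite bar, lidocaine; within) x task (orthographic, phonological) x word type (4), for response time and for accuracy. **Picture model:** reader group x condition.
2. **Objective 1:** do not make it conditional on a 4-way interaction. Pre-specify each perturbation against none in the dyslexia group, per word type as the primary endpoint is worded: 3 x 2 x 4 x 2 = 48 contrasts, Bonferroni 0.05/48 = 0.0010. If the sponsor prefers to average over word type, the family is 12 (0.05/12 = 0.0042) and the endpoint wording should say so.
3. **Other comparators:** state whether lidocaine versus lollipop and versus bite bar belong to the family. Including them gives 80 contrasts (0.05/80 = 0.0006), or 20 if averaged (0.05/20 = 0.0025).
4. **Controls and Objective 2:** name reader group x condition as the concurrent-control test, and say how the comparison with the earlier study will be made, even if only descriptively.
5. **Order:** state that lidocaine versus none is confounded with order. The protocol fixes the position deliberately: "The lidocaine condition will always be lastly completed so its effects will not interfere with the other conditions". With lidocaine in last place for everyone, an order term cannot separate the two.
6. **Trigger:** replace the 30-subject trigger with one that matches 30 + 30.

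**Cost.** SAP text only, with no new procedures. On the assumptions above, the detectable effect moves from 0.75 to 0.83 SD per word type, or from 0.64 to 0.73 if averaged. With the two extra comparators it is 0.87 or 0.77. These comparisons assume that the current, unstated Bonferroni family is lidocaine versus none only. If the 30-subject trigger was intended, analysis waits for all 60.

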
(2014) reported that sensory cueing approaches (which place emphasis on the relation between movements and auditory and somatosensory information via auditory, and touch, pressure, kinesthetic and proprioceptive cues) are the most effective for treatment of CAS. Such results suggest that sensory cueing approaches either target the underlying impairment directly (i.e. restorative) or compensate for deficits (i.e. compensatory). The identification of sensory difficulties in children with CAS is important to understand speech characteristics and treatment efficacy in this population. These findings warrant additional investigations to understand if and to what extent somatosensory processing contributes to speech production and reading deficiencies in healthy and impaired adult and pediatric populations.

We have also previously attempted to determine the influence of speech production feedback on reading performance by measuring reading performance in adults while adding an additional motor component (i.e., lollipop, bite bar, lidocaine). These somatosensory perturbations have the potential to alter and/or decrease the sensory feedback from the articulators in the mouth.

We found that the lollipop had a facilitatory effect (i.e., faster response times) in the orthographic lexical decision tasks but no effect on the phonological lexical decision tasks or picture categorization tasks. In contrast, the lidocaine had a facilitatory effect (i.e., faster response times) in the phonological lexical decision tasks, but no facilitatory effects on the orthographic lexical decision tasks or picture categorization. Finally, the bite bar did not impact performance in any of the three tasks. However, we do not know if these effects (i.e., lollipop, bite bar, lidocaine) hold for an adult population with reading disorders.

The investigational product we are requesting approval to use is Lidocaine Hydrochloride Oral Topical Solution 2% USP. This oral topical anesthetic will temporarily numb the participant's articulators. This clinical trial will be conducted in compliance with this described protocol, GCP and the applicable regulatory requirement(s).

Purpose | Objectives

1. To determine the effects of three different somatosensory perturbations (i.e., lollipop, bite bar, lidocaine) on reading performance (i.e., speed, accuracy) in adults with dyslexia.

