Women of childbearing potential (WOCBP), i.e. assigned at birth females who experienced menarche and are not sterile or postmenopausal, may be included in the study, provided that they use an acceptable method of contraception, such as: hormonal contraceptives (e.g. combined oral contraceptives, patch, vaginal ring, injectables, and implants); intrauterine device (IUD) or intrauterine system (IUS); (partner's) vasectomy, tubal ligation; double barrier methods of contraception (e.g. male condom plus spermicide, cervical cap plus spermicide, diaphragm plus spermicide). Abstinence is acceptable provided that it is consistent with the participant's usual lifestyle.

Adult participants must weigh at least 50 kg or 110 lbs to avoid any possible toxic effects from the lidocaine.

Qualified Investigator (QI) Physician:

[name], MD

[name]

[name]

[name]

Edmonton, AB

[contact]

[contact]

Subjects that do not meet these criteria when contacting researchers will not be scheduled for collection. Participants will be immediately withdrawn (i.e., collection stopped) if they are unable to perform reading assessments, they report any adverse reaction or a desire to discontinue. If the participant withdraws or their participation discontinued, their data will be retained for analysis, unless the participant requests the data be destroyed. Any withdrawn participants will be replaced with additional recruitment. No follow-up is planned for withdrawn

participants unless they experience an adverse reaction that require medical follow-up and reporting.

[figure not shown]

Figure 1. Schematic of repeated measures design

Methodology

The primary endpoint is reading response time and accuracy for each word type with and without oral perturbation.

The individual will be required to attend one collection session at the Clinical Sciences Building at the University of Alberta which will last no more than 90-minutes. Twenty percent (i.e., 12) of recruited participants will complete the the protocol below over two separate 60-minute sessions to investigate the effects of order, fatigue, etc.

During the session, participants will:

1. Read and complete an information and consent form (less than 10 minutes to complete).
2. Complete a pre-collection questionnaire to gather information such as age, sex and allergies (less than 5 minutes to complete).

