3. Any participant reporting a personal or family history of adverse reactions to anesthetics will not be enrolled. If a participant reports any concerns or adverse reactions during the collection session, collection will immediately stop, and their participation discontinued.
4. If the participant is enrolled, they will be assigned a randomly generated identification number. All of their files and documents will be labelled with this number.
5. Each participant will also be randomly assigned to one of six possible task orders. Neither participants nor experimenters will be blinded to these conditions. This is documented in a hard-copy log.
6. Participants will be fit with an fNIRS cap to measure brain signals.
7. Then complete three computer generated tasks under four conditions (a, b and c will be randomized):
 - a. No sensory perturbation
 - b. Lollipop
 - c. Bite bar
 - d. Lidocaine – this condition will always be completed last.

8. The comparators to the lidocaine are no sensory perturbation, a candy lollipop and candy bite bar. All candy is obtained from the grocery store and are individually packaged. The lidocaine will be dispensed by a pharmacist and administered by the research team.
9. For the three computer generated tasks (randomly administered), accuracy and response time will be measured by the computer:
 - a. Task 1 (orthographic lexical decision): involves deciding whether a series of letters formulates a word or a nonword. Individuals will press the 'g' key if it is a word and the 'h' key if it is a nonword. Stimuli are single, monosyllabic, 4-7 letter length, words and nonwords.
 - b. Task 2 (phonological lexical decision): involves deciding whether a series of letters sounds out a word or a nonword. Individuals will press the 'g' key if it is a word and the 'h' key if it is a nonword. Stimuli are single, monosyllabic, 4-7 letter length, words and nonwords.
 - c. Task 3 (picture categorization): requires participants to make a judgement about whether a visually presented object is an animal or not. They will press 'g' if the object is an animal, and 'h' if it is not an animal.
10. Complete a short questionnaire rating and describing the numbness caused by the lidocaine (less than 5 minutes to complete).

Treatment

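### The two-level time factor does not fit the four-condition design: its 'pre' level is undefined, read literally it mixes the candy blocks with no perturbation, and no term estimates the lollipop or bite-bar effect

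*Combined protocol and SAP*

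**What the plan says.** Objective 1 is "To determine the effects of three different somatosensory perturbations (i.e., lollipop, bite bar, lidocaine) on reading performance" in adults with dyslexia. The Methodology section defines the endpoint to match: "The primary endpoint is reading response time and accuracy for each word type with and without oral perturbation".

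Methodology step 7 sets out the testing: "Then complete three computer generated tasks under four conditions (a, b and c will be randomized"), followed by "Lidocaine – this condition will always be completed last". Step 8 adds: "The comparators to the lidocaine are no sensory perturbation, a candy lollipop and candy bite bar". It does not say whether these comparators are used separately or combined.

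The Statistical Analysis section opens with an ANOVA on group, task, word type and "time (pre-lidocaine vs. post-lidocaine), as the factors of interest". If the four-way interaction is significant, mixed ANOVAs follow for each reading task, and there the label changes: "The independent variables will be time (pre-perturbation vs. post-perturbation), word type (exception, regular, pseudohomophone, nonword) and group". The picture-task ANOVA uses the second label too. Bonferroni-corrected t-tests then explore lidocaine effects. Neither label is tied to conditions (a) to (d), and no model has a term for lollipop or bite bar.

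**The concern.** The endpoint and objective 1 need each perturbation compared with no perturbation. A two-level factor cannot supply three such effects, whatever its levels contain.

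The lidocaine effect itself is also not pinned down. Because lidocaine always comes last, every other block is pre-lidocaine in time. On that reading the reference is one third no perturbation and two thirds candy conditions, and the test is no longer of lidocaine against no perturbation. An analyst could equally take condition (a) alone and leave the candy blocks out. The two choices test different null hypotheses, and nothing stops the choice being made after the data are seen.

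The choice could matter because the Background reports a lollipop effect confined to one task: "We found that the lollipop had a facilitatory effect (i.e., faster response times) in the orthographic lexical decision tasks", with none in the phonological or picture tasks. A reference containing the lollipop block would make lidocaine look relatively slower in the orthographic task only. That could hide an orthographic benefit, or produce a task difference resembling the earlier lidocaine finding, which was a benefit in the phonological task only.

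**Working it through.** The plan gives no effect size, standard deviation, alpha or power for this comparison, so there is no figure of its own to reproduce.

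**1. Does either label identify condition (a)?** Conditions a, b and c (none, lollipop, bite bar) have 3! = 6 orders. Condition (a) comes first in 2 of them. In the other 4, at least one candy block precedes it. So pre-perturbation, read by time, does not pick out the no-perturbation block. Pre-lidocaine, read by time, picks out all three blocks in every order.

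**2. What each reference estimates.** Let d be the mean of a condition minus the mean under no perturbation.

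| Pre level | Lidocaine contrast |
|---|---|
| (a) only | d_lido |
| average of a, b and c | d_lido − (d_lolli + d_bite)/3 |

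**3. Direction, from the Background results.** The bite bar had no effect in any task, so d_bite = 0.
- Orthographic task: d_lolli is negative (faster responses). The pooled contrast is d_lido − d_lolli/3. If the lollipop speeds responses by 1 unit and lidocaine does nothing, lidocaine appears 0.33 units slower.
- Phonological and picture tasks: d_lolli = 0, so there is no shift.

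**4. Which planned tests are affected?** The shift of −d_lolli/3 enters a within-task time main effect and the t-tests for the orthographic task. The four-way interaction takes differences across group, task, word type and time together. A lollipop effect that varies by task but is equal across word types and groups subtracts out of it. A lollipop effect common to both groups likewise subtracts out of any group-by-time test.

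**5. Illustration for a simple paired lidocaine contrast.** Assumptions: two-sided 5%, n = 30, independent block residuals with SD 1, no order effect, no true lidocaine or bite-bar effect. A paired lollipop effect of dz corresponds to a mean shift of dz × √2. The pooled contrast has bias dz × √2/3 and SD √(1 + 1/3) = 1.155. The noncentrality is (bias/1.155) × √30.

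| Lollipop dz | Shift | Bias | Noncentrality | False-positive rate |
|---|---|---|---|---|
| 0.3 | 0.424 | 0.141 | 0.67 | 10% |
| 0.5 | 0.707 | 0.236 | 1.12 | 19% |
| 0.8 | 1.131 | 0.377 | 1.79 | 41% |

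With condition (a) as the reference, the rate is 5% in every row.

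**6. What the single reference costs.** Suppose only lidocaine is active, with dz 0.5 against (a) and n = 30. Against (a), the noncentrality is 0.5 × √30 = 2.74 and power is about 75%. Against the average of three blocks it is (0.707/1.155) × √30 = 3.35 and power is about 90% (89% by simulation).

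**The case against.** Pooling is not stated. Nothing in the Statistical Analysis section says the three earlier blocks are averaged, and step 8 lists comparators without combining them. The pre-perturbation label and the endpoint wording both fit a reference made of condition (a) alone. A reader might infer that the plan commits to testing lidocaine against a mix of other perturbations. The documents do not support that: pooling is the literal reading of one of two labels, and even then the no-perturbation block is in the mix. This part of the objection stands. The ambiguity remains.

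A reader might also infer that the planned omnibus test has an inflated error rate of the size shown. It does not follow. The omnibus gate is a four-way interaction, and the earlier lollipop effect is reported by task only, so on that pattern the gate is not shifted. The figures describe a paired contrast.

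Nor can one conclude that pooling would cancel most of any real effect. That needs all three perturbations to act alike, and the Background reports otherwise: the bite bar did nothing, and lollipop and lidocaine helped different tasks. In the phonological task, where lidocaine helped before, pooling would cause no bias and would add precision.

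Finally, the time labels can be seen as part of a wider mismatch: the section describes lidocaine and no-lidocaine groups, while every participant receives lidocaine. That is a fair description, but correcting the group factor alone would leave the reference level undefined and two perturbations without a term.

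**Conclusion.** The concern holds in this form: the two-level factor is not mapped to the four conditions, carries two labels that do not mean the same thing, and leaves the lollipop and bite-bar effects without a test although objective 1 names them. That much follows from the text alone.

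The bias is conditional. If the earlier blocks are averaged, the lidocaine contrast shifts by one third of the summed candy effects. On the sponsor's earlier results in typical readers, this touches only the orthographic within-task comparisons. Whether those results carry over to adults with dyslexia is what the trial sets out to learn. The 10%, 19% and 41% rates rest on assumed effect sizes and a simplified residual structure. They show that the choice of reference can matter; they do not forecast the trial's error rate.

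The plan should be changed before the data are analysed.

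**What to change.** In the Statistical Analysis section:
- Replace the two-level time factor with a four-level within-subject condition factor (none, lollipop, bite bar, lidocaine) in the omnibus, follow-up and picture-task ANOVAs. Name condition (a), no perturbation, as the reference throughout.
- Prespecify Bonferroni-corrected contrasts of each perturbation against (a), and state how many tests each correction covers. Make lidocaine versus lollipop and lidocaine versus bite bar secondary.
- State that the candy blocks are never pooled into the reference.

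Renaming the reference while keeping two levels would not be enough, because lollipop versus none and bite bar versus none would still go untested.

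All four blocks are already part of the session, so the change is to wording and analysis code only. The price is precision: one reference block is noisier than the mean of three (about 75% power instead of about 89% to 90% in the case worked above, where lidocaine alone is active). The change does not resolve the group-factor mismatch or the fixed last position of lidocaine, which need separate attention.
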